6.3.2 Administration

The dose of oxaliplatin will be 130 mg/m² given on day 1 of a 3-week cycle, except in the "biomarker cycle" (i.e. first cycle for subjects in the dose expansion cohort). During the biomarker cycle, oxaliplatin will be given on Day 8 (to allow for one week of pembrolizumab monotherapy for biomarkers). A treatment window of +/- 3 days of day 1 is allowed for cycle 2 and all subsequent cycles.

It is preferable but not mandatory that oxaliplatin infusion should be administered before pembrolizumab on days when both drugs are given.

Oxaliplatin must be infused either by peripheral vein or central venous line over 2 hours. Infusion lines should be adequately flushed with 5% dextrose solution between the administrations of any other drugs. The administration of oxaliplatin does not require pre-hydration. Oxaliplatin should not be administered with saline or other chloride containing solutions. Oxaliplatin is unstable in the presence of chloride.

6.4 Capecitabine

Capecitabine will be obtained from commercial sources; the cost of capecitabine will be billed to the subject and/or subject's insurance.

Capecitabine is a fluoropyrimidine carbamate with antineoplastic activity. It is an orally administered systemic prodrug of 5'-deoxy-5-fluorouridine (5'-DFUR) which is converted to 5-fluorouracil. The chemical name for capecitabine is 5'-deoxy-5-fluoro-N-[(pentyloxy) carbonyl]-cytidine and has a molecular weight of 359.35. Capecitabine is a white to off-white crystalline powder with an aqueous solubility of 26 mg/mL at 20°C.

Capecitabine is supplied as biconvex, oblong film-coated tablets for oral administration. Each peach-colored tablet contains 500 mg capecitabine. The inactive ingredients in capecitabine include: anhydrous lactose, croscarmellose sodium, hydroxypropyl methylcellulose, microcrystalline cellulose, magnesium stearate and purified water. The peach or light peach film coating contains hydroxypropyl methylcellulose, talc, titanium dioxide, and synthetic yellow and red iron oxides.

6.4.1 Storage and Handling

Capecitabine tablets should be stored at 25°C (77°F); excursions permitted to 15° to 30°C (59° to 86°F). The container should be kept tightly closed.

Care should be exercised in the handling of capecitabine. Capecitabine tablets should not be cut or crushed. Procedures for the proper handling and disposal of anticancer drugs should be considered.

6.4.2 Administration

At the discretion of the treating physician, the patient may receive 850mg/m² or 1000mg/m² of capecitabine. Capecitabine will be administered at a dose of 850/1000 mg/m² twice daily, for a total daily dose of 1700/2000 mg/m² beginning the morning of Day 1 of each 3-week cycle and continuing through the evening of Day 14; except in the "biomarker cycle" (i.e. first cycle for subjects in the dose expansion cohort). During the biomarker cycle, capecitabine will begin on Day 8 (to allow for one week of pembrolizumab monotherapy for biomarkers). A treatment window of +/- 3 days of day 1 is allowed for cycle 2 and all subsequent cycles.

See current capecitabine package insert for dosing instructions in patients with moderate renal impairment.

The dose of capecitabine will be calculated on the basis of milligrams of drug per square meter (mg/m²) of body surface area (BSA). The dose of capecitabine will be rounded to the nearest dose that can be obtained by using the 500 mg tablets. Since capecitabine tablets cannot be split, patients may take different numbers of pills in the morning and evening in order to achieve the appropriate dose. The following is an example of how dose rounding may be performed:

Explanation: $[\{BSA\} m^2 \times \{dose level\} mg/m^2] \times 2 = \text{Daily Dose mg}$
Daily Dose mg $\div 500$ mg tablet = number of tablets per day, rounded to whole tablets
Divide number of whole tablets per day into 2 doses for morning (AM) and evening (PM)

Calculation: $[1.68m^2 \times 1000mg/m^2] \times 2 = 3360mg$
 $3360mg \div 500mg$ tablet = 6.72 tablets per day, rounded to 7 tablets per day
Divide 7 tablets into 2 doses = three 500mg tablets in AM and four 500mg tablets in PM

The dose will be recalculated per institutional standard (e.g., based on the new body surface area prior to the start of each cycle only if the weight changes by 10% from baseline).

Capecitabine will be taken orally. The total daily dose should be taken as two divided doses approximately 12 hours apart, within 30 minutes after the ingestion of food, ideally after breakfast and the evening meal. Tablets should be swallowed with approximately 200 ml of water (not fruit juices). Tablets are not scored and should not be split. If needed, capecitabine may be dissolved for administration either orally or via G or J tube but patient must receive safety handling training from pharmacy personnel.

6.5 Concomitant Medications/Vaccinations

Concomitant medications will be documented throughout the study. Medications or vaccinations specifically prohibited in the exclusion criteria are not allowed during the ongoing trial. If there is a clinical indication for one of these or other medications or vaccinations specifically prohibited during the trial, discontinuation from trial therapy or vaccination may be required. The Investigator should discuss any questions regarding this with the Lead PI.

6.5.1 Acceptable Concomitant Medications

All treatments that the Investigator considers necessary for a subject's welfare may be administered at the discretion of the Investigator in keeping with the local standards of medical care. All concomitant medication received from the date of signed informed consent through 30 days after the last dose of study drug should be recorded on the CRF including all prescription, over-the-counter (OTC), herbal supplements, and IV medications.

Abstinence is acceptable if this is the usual lifestyle and preferred contraception for the subject. Otherwise, subjects must agree to use two birth control methods after informed consent is signed through 120 days after the last dose of study drug. The two methods can either be two barrier methods or a barrier method plus a hormonal method to prevent pregnancy. The following are considered adequate barrier methods of contraception: diaphragm with spermicide (cannot be used in conjunction with cervical cap/spermicide), cervical cap with spermicide (nulliparous women only), contraceptive sponge (nulliparous women only), and male condom or female condom (cannot be used together). Appropriate hormonal contraceptives will include oral contraceptive pill (estrogen/progestin pill or progestin-only pill), contraceptive skin patch, vaginal contraceptive ring, or subcutaneous contraceptive injection.

6.5.2 Prohibited Concomitant Medications

Subjects are prohibited from receiving the following therapies during the Screening and Treatment Period of this study:

- Antineoplastic systemic chemotherapy or biological therapy
- Immunotherapy not specified in this protocol
- Chemotherapy not specified in this protocol
- Investigational agents other than pembrolizumab
- Radiation therapy to target lesions. If subject needs palliative local radiation (e.g., for relief of dysphagia or of pain from bony metastases), protocol therapy may be delayed with the

approval of the lead PI. Radiation therapy must be completed for at least 14 days prior to resumption of protocol treatment.

- Live vaccines within 30 days prior to the first dose of study drug and while participating in the study. Examples of live vaccines include, but are not limited to, the following: measles, mumps, rubella, varicella/zoster, yellow fever, rabies, BCG, and typhoid vaccine.
- Systemic glucocorticoids for any purpose other than to modulate symptoms from an event of clinical interest of suspected immunologic etiology. Prophylactic dosing of steroids prior to treatment and administration of low dose steroids for up to 48 hours post treatment is permitted. Corticosteroids administered as pre-medication for IV contrast allergy are also allowed.

Subjects who, in the assessment by the Investigator, require the use of any of the aforementioned treatments for clinical management should be removed from the trial. Subjects may receive other medications that the Investigator deems to be medically necessary.

There are no prohibited therapies during the Follow-up Period.

7.0 DOSE MODIFICATION AND TOXICITY MANAGEMENT

Subjects will be monitored continuously for AEs throughout the study and for 30 days after the last dose of study drug. Subjects will be instructed to notify their treating physician of any and all AEs. Toxicity will be graded according to NCI-CTCAE version 4.0.

All AEs should also be managed with supportive care at the earliest signs of toxicity considered related to study drug(s).

7.1 Dose Modifications

Subjects experiencing one or more AEs due to the study drug(s) may require dose modification(s) as described in [Section 7.1.1](#) and [Section 7.1.2](#). At the discretion of the Investigator, dose modifications are permitted outside of the those provided in the protocol if the Investigator feels it is in the interest of the subject's safety (e.g., due to multiple toxicities, persistent toxicities, intercurrent illness, or short term compliance or monitoring issues, etc.).

Subjects may need to be followed at least weekly when any study drug is held for toxicity until the toxicity returns to Grade ≤ 1 or is determined to be chronic or irreversible.

Dosing interruptions are permitted in the case of medical / surgical events or logistical reasons not related to study therapy (e.g., elective surgery, unrelated medical events, patient vacation, and/or holidays). Subjects should be placed back on study therapy within 4 weeks of the scheduled interruption, unless otherwise discussed with the Lead PI. The reason for interruption should be documented in the patient's study record. Dosing may be interrupted if there is a need for local palliative radiation therapy, with the approval of the lead PI. In this case, protocol-based therapy cannot be resumed until patients are at least 14 days out from the end of radiation.

If pembrolizumab is permanently discontinued, the subject will be discontinued from study treatment. Maximum duration of treatment for pembrolizumab will be up to 35 cycles. If patients discontinue oxaliplatin due to intolerance, they can be maintained on capecitabine and pembrolizumab. If capecitabine is not tolerated, pembrolizumab monotherapy may be continued. Re-introduction of oxaliplatin is permitted provided neuropathy has improved.

All dose modifications and reasons for modification must be recorded in the CRF.

7.1.1 Pembrolizumab Dose Modifications

Adverse events (both non-serious and serious) associated with pembrolizumab exposure may represent an immunologic etiology. These adverse events may occur shortly after the first dose or several months after the last dose of treatment.

Pembrolizumab must be withheld for treatment-related toxicities as per Table 7.1.1. There are no dose reductions for pembrolizumab.

Note: Subject must be permanently discontinued for any severe or Grade 3 treatment-related toxicity that recurs or any life-threatening event unless otherwise specified in Table 7.1.1.

General Instructions:

1. Corticosteroid taper should be initiated upon AE improving to Grade 1 or less and continue to taper over at least 4 weeks.
2. For situations where pembrolizumab has been withheld, pembrolizumab can be resumed after AE has been reduced to Grade 1 or 0 and corticosteroid has been tapered. Pembrolizumab should be permanently discontinued if AE does not resolve within 12 weeks of last dose or corticosteroids cannot be reduced to ≤ 10 mg prednisone or equivalent per day within 12 weeks.
3. For severe and life-threatening irAEs, IV corticosteroid should be initiated first followed by oral steroid. Other immunosuppressive treatment should be initiated first followed by oral steroid. Other immunosuppressive treatment should be initiated if irAEs cannot be controlled by corticosteroids.

Table 7.1.1 Pembrolizumab Dose Modifications

Immune-related AEs	Toxicity grade or conditions (CTCAEv4.0)	Action taken to pembrolizumab	irAE management with corticosteroid and/or other therapies	Monitor and follow-up
Pneumonitis	Grade 2	Withhold	
 • Administer corticosteroids (initial dose of 1-2 mg/kg prednisone or equivalent) followed by taper 	
 • Monitor participants for signs and symptoms of pneumonitis • Evaluate participants with suspected pneumonitis with radiographic imaging and initiate corticosteroid treatment • Add prophylactic antibiotics for opportunistic infections
	Grade 3 or 4, or recurrent Grade 2	Permanently discontinue		
Diarrhea / Colitis	Grade 2 or 3	Withhold	
 • Administer corticosteroids (initial dose of 1-2 mg/kg prednisone or equivalent) followed by taper 	
 • Monitor participants for signs and symptoms of enterocolitis (ie, diarrhea, abdominal pain, blood or mucus in stool with or without fever) and of bowel perforation
	Grade 4	Permanently discontinue		

Immune-related AEs	Toxicity grade or conditions (CTCAEv4.0)	Action taken to pembrolizumab	irAE management with corticosteroid and/or other therapies	Monitor and follow-up
				
(ie, peritoneal signs and ileus).
 
 Participants with \geq Grade 2 diarrhea suspecting colitis should consider GI consultation and performing endoscopy to rule out colitis. Participants with diarrhea/colitis should be advised to drink liberal quantities of clear fluids. If sufficient oral fluid intake is not feasible, fluid and electrolytes should be substituted via IV infusion.
AST / ALT elevation or Increased bilirubin	Grade 2	Withhold	Administer corticosteroids (initial dose of 0.5- 1 mg/kg prednisone or equivalent) followed by taper	Monitor with liver function tests (consider weekly or more frequently until liver enzyme value returned to baseline or is stable)
	Grade 3 or 4	Permanently discontinue	Administer corticosteroids (initial dose of 1-2 mg/kg prednisone or equivalent) followed by taper	
Type 1 diabetes mellitus (T1DM) or Hyperglycemia	Newly onset T1DM or Grade 3 or 4 hyperglycemia associated with evidence of β -cell failure	Withhold	
 Initiate insulin replacement therapy for participants with T1DM Administer anti-hyperglycemic in participants with hyperglycemia 	
 Monitor participants for hyperglycemia or other signs and symptoms of diabetes.
Hypophysitis	Grade 2	Withhold	
 Administer corticosteroids and initiate hormonal replacements as clinically indicated. 	
 Monitor for signs and symptoms of hypophysitis (including hypopituitarism and adrenal insufficiency)
	Grade 3 or 4	Withhold or permanently discontinue ¹		
Hyperthyroidism	Grade 2	Continue	Treat with non-selective beta-blockers (eg, propranolol) or thionamides as appropriate	
 Monitor for signs and symptoms of thyroid disorders.
	Grade 3 or 4	Withhold or permanently discontinue ¹		

Immune-related AEs	Toxicity grade or conditions (CTCAEv4.0)	Action taken to pembrolizumab	irAE management with corticosteroid and/or other therapies	Monitor and follow-up
Hypothyroidism	Grade 2	Continue	Initiate thyroid replacement hormones (eg, levothyroxine or liothyroinine) per standard of care	
 Monitor for signs and symptoms of thyroid disorders.
Nephritis and Renal dysfunction	Grade 2	Withhold	Administer corticosteroids (prednisone 1-2 mg/kg or equivalent) followed by taper.	
 Monitor changes of renal function
	Grade 3 or 4	Permanently discontinue		
Myocarditis	Grade 1 or 2	Withhold	Based on severity of AE administer corticosteroids	
 Ensure adequate evaluation to confirm etiology and/or exclude other causes
	Grade 3 or 4	Permanently discontinue		
All other immune-related AEs	Intolerable/persistent Grade 2	Withhold	Based on type and severity of AE administer corticosteroids	
 Ensure adequate evaluation to confirm etiology and/or exclude other causes
	Grade 3	Withhold or discontinue based on the type of event. Events that require discontinuation include and not limited to: Gullain-Barre Syndrome, encephalitis		
	Grade 4 or recurrent Grade 3	Permanently discontinue		

¹Withhold or permanently discontinue pembrolizumab at the discretion of the investigator or treating physician.

NOTE: For participants with Grade 3 or 4 immune-related endocrinopathy where withhold of pembrolizumab is required, pembrolizumab may be resumed when AE resolves to ≤Grade 2 and is controlled with hormonal replacement therapy or achieved metabolic control (in case of T1DM).

7.1.2 XELOX Dose Modifications

Toxicity Grade ^a	Occurrence	Oxaliplatin	Capecitabine
DIARRHEA			
Grade 1	Any	Maintain dose	Maintain dose

Grade 2	Any	If tolerable: Maintain dose If intolerable: Hold until grade ≤ 1 , then resume at 80% of current dose	If tolerable: Maintain dose If intolerable: Hold until grade ≤ 1 , then resume at 80% of current dose ^b
Grade 3	1 st – 3 rd	Hold until grade ≤ 1 , then resume at 80% of current dose	Hold until grade ≤ 1 , then resume at 80% of current dose
	4 th and higher	Hold until grade ≤ 1 , –obtain permission of PI to resume at 80% of current dose	Hold until grade ≤ 1 , obtain permission of PI to resume at 80% of current dose–
Grade 4	1 st	Hold until grade ≤ 1 , then resume at 60% of current dose	Hold until grade ≤ 1 , then resume at 60% of current dose
	2 nd and higher	Hold until grade ≤ 1 , obtain permission of PI to resume at 60% of current dose ^b	Hold until grade ≤ 1 , obtain permission of PI to resume at 60% of current dose ^b

VOMITING			
Grade 1	Any	Maintain dose	Maintain dose
Grade 2	Any	Maintain dose	Maintain dose
Grade 3 [occurring within 3 days of Oxaliplatin dosing despite optimal anti-emetic prophylaxis]	1 st	Hold until grade ≤ 1 , then resume at 80% of current dose ^c	Maintain dose
	2 nd and higher	Hold until grade ≤ 1 , then resume at current dose. ^c	Maintain dose
Grade 4 (TPN, intensive care or hemodynamic collapse) [occurring within 3 days of Oxaliplatin dosing despite optimal anti-emetic prophylaxis]	1 st	Hold until grade ≤ 1 ^c , then resume at 60% of current dose	Hold until grade ≤ 1 , then resume at 60% of current dose
	2 nd and higher	Discontinue	Hold until grade ≤ 1 , obtain permission of PI to resume at 60% of current dose

a. National Cancer Institute Common Terminology Criteria Version 3.
 b. Continue treatment if it is considered to be in the best interest of the patient
 c. **NOTE:** After Cycle 1, at the discretion of the treating physician, once there is recovery of the toxicity to grade ≤ 1 , the treating physician may choose, to hold oxaliplatin and continue capecitabine and pembrolizumab at current dose as clinically indicated. If the treating physician chooses to restart oxaliplatin later in the patient's treatment course, the dose of oxaliplatin at which the patient restarts should be one dose level lower than last dose level on which patient was treated. The specific treatment approach used and dose modifications that occur are required to be reported in the Case Report Forms.

OTHER CLINICALLY SIGNIFICANT* NON-HEMATOLOGIC ADVERSE EVENTS			
ToxicityGrade^a	Occurrence	Oxaliplatin	Capecitabine
Grade 1	Any	Maintain dose	Maintain dose
Grade 2	1 st	Hold until grade ≤ 1 , then resume at 80% of current dose ^c	Hold until grade ≤ 1 , then resume at 80% of current dose

OTHER CLINICALLY SIGNIFICANT* NON-HEMATOLOGIC ADVERSE EVENTS			
ToxicityGrade^a	Occurrence	Oxaliplatin	Capecitabine
	2 nd and higher	Hold until grade ≤ 1, then resume at current dose. ^{b,c}	Hold until grade ≤ 1, then resume at 80% of current dose
Grade 3	1 st	Hold until grade ≤ 1, then resume at 80% of current dose ^c	Hold until grade ≤ 1, then resume at 80% of current dose
	2 nd and higher	Hold until grade ≤ 1, then resume at current dose. ^{b,c}	Hold until grade ≤ 1, then resume at 80% of current dose
Grade 4	1 st	Hold until grade ≤ 1, then resume at 60% of current dose ^c	Hold until grade ≤ 1, then resume at 60% of current dose
	2 nd and higher	Hold until grade ≤ 1, obtain permission of PI to resume at 60% of current dose ^b	Hold until grade ≤ 1, obtain permission of PI to resume at 60% of current dose ^b

a. National Cancer Institute Common Terminology Criteria Version 3.0

b. Continued treatment if it is considered to be in the best interest of the patient.

c. **NOTE:** After Cycle 1, at the discretion of the treating physician, once there is recovery of the toxicity to grade ≤ 1, the treating physician may choose, instead of lowering the dose of capecitabine, to hold oxaliplatin and continue capecitabine and pembrolizumab at current dose as clinically indicated. If toxicity recurs, follow original dose modification instructions for capecitabine. If the treating physician chooses to restart oxaliplatin later in the patient's treatment course, the dose of oxaliplatin at which the patient restarts should be one dose level lower than last dose level on which patient was treated. The specific treatment approach used and dose modifications that occur are required to be reported in the Case Report Forms.

* Dose adjustments only for clinically significant toxicities (e.g. asymptomatic lab abnormalities do not necessarily require dose modifications) If non-hematologic toxicities can be attributed solely to either oxaliplatin, capecitabine, or pembrolizumab then no dose adjustments of the other agents are needed.

HEMATOLOGIC ADVERSE EVENTS			
ToxicityGrade ^a	Occurrence	Oxaliplatin	Capecitabine
NEUTROGENIA			
Grade 1	Any	Maintain dose	Maintain dose
Grade 2	Any	Maintain dose	Maintain dose
Grade 3($\geq 0.5 - < 1 \times 10^9 /L$)	1 st	Hold until grade ≤ 1 , then resume at current dose	Maintain dose
	2 nd and higher	Hold until grade ≤ 1 , then resume at 80% of current dose ^d	Maintain dose
Grade 4 ($< 0.5 \times 10^9 /L$)	1 st	Hold until grade ≤ 1 , then resume at 80% of current dose ^{b,c,d}	Hold until grade ≤ 1 , then resume at 80% of the current dose ^{b,c}
	2 nd and higher	Hold until grade ≤ 1 , obtain permission of PI to resume at 60% of current dose ^d	Hold until grade ≤ 1 , obtain permission of PI to resume at 60% of current dose
FEBRILE NEUTROGENIA			
Grade 3 (neutropenia and fever $\geq 38.5C$)	1 st – 2 nd	Hold until resolution of fever and neutropenia to grade ≤ 1 , then resume at 60% of current dose ^d	Hold until resolution of fever and neutropenia to grade ≤ 1 , then resume at 60% of current dose ^{b,c,d}
	3 rd	Discontinue Protocol Therapy	Discontinue Protocol Therapy
Grade 4 (neutropenia and fever $> 38.5 C$)	Any	Discontinue Protocol Therapy	Discontinue Protocol Therapy
THROMBOCYTOPENIA			
Grade 1 ($< LLN - < 75.0 \times 10^9 /L$)	Any	Maintain dose	Maintain dose
Grade 2($\geq 50.0 - < 75.0 \times 10^9 /L$)	1 st	Hold until grade ≤ 1 , then resume at 80% of current dose ^d	Maintain dose
	2 nd and higher	If stable grade 2, maintain current dose	Maintain dose
Grade 3($\geq 25.0 - < 50.0 \times 10^9 /L$)	1st	Hold until grade ≤ 1 , then resume at 80% current dose ^d	Hold until grade ≤ 1 , then resume at 80% of the current dose
	2nd and higher	Hold until grade ≤ 1 , then resume at 80% current dose ^d	Hold until grade ≤ 1 , then resume at 80% of the current dose ^b
Grade 4($< 25.0 \times 10^9 /L$)	1st	Hold until grade ≤ 1 , then resume at 60% of the current dose ^{b,d}	Hold until grade ≤ 1 , then resume at 60% of the current dose ^b
	2nd	Discontinue Protocol Therapy	Discontinue Protocol Therapy

HEMOGLOBIN			
Grade 1 < LLN - 10.0 g/dL < LLN - 100 g/L < LLN - 6.2mmol/L	Any	Maintain dose	Maintain dose ^b
Grade 2 8.0 - < 10.0 g/dL 80 - < 100 g/L 4.9 - < 6.2 mmol/L	Any	Maintain dose	Maintain dose
Grade 3 6.5 - < 8.0 g/dL 65 - < 80 g/L 4.0 - < 4.9 mmol/L	Any	Maintain dose	Maintain dose
Grade 4 < 6.5 g/dL < 65 g/L < 4.0 mmol/L	Any	Hold until \leq grade 2; then resume at current dose, may transfuse ^b	Maintain dose ^b
OTHER HEMATOLOGIC TOXICITY			
Grades 1 - 4	Any	Maintain dose	Maintain dose

- a. National Cancer Institute Common Terminology Criteria Version 3.0
- b. Continued treatment only if it is considered to be in the best interest of the patient
- c. Consider growth factor support if continuing treatment is felt to be in the patient's best interest.
- d. **NOTE:** After Cycle 1, at the discretion of the treating physician, once there is recovery of the toxicity to grade ≤ 1 , the treating physician may choose, to hold oxaliplatin and continue capecitabine and pembrolizumab at current dose as clinically indicated. If the treating physician chooses to restart oxaliplatin later in the patient's treatment course, the dose of oxaliplatin at which the patient restarts should be one dose level lower than last dose level on which patient was treated. The specific treatment approach used and dose modifications that occur are required to be reported in the Case Report Forms.

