3.2.1 Dose Limiting Toxicity

Using the NCI-CTCAE version 4.0, the following adverse events will be considered dose limiting toxicity (DLT) if occurring during the first cycle (21 days) of treatment and deemed to be related to study treatment:

- Grade 4 neutropenia, thrombocytopenia or anemia.
- Grade ≥ 3 neutropenia or thrombocytopenia lasting over 7 days.
- Grade 3 thrombocytopenia associated with bleeding.
- Neutropenic fever.
- Grade ≥ 3 nausea/vomiting or diarrhea lasting ≥ 3 days despite adequate supportive measures.
- Grade ≥ 3 ALT, AST, or bilirubin elevation > 7 days.
- Grade ≥ 3 non-hematologic toxicity excluding alopecia, anorexia, fatigue, hypertension, isolated lab abnormalities (not clinically significant) and/or allergic or idiosyncratic reactions to any of the study drugs. Anorexia, fatigue and hypertension will be considered as DLT only if they reach Grade 4 or are considered unmanageable.
- Treatment delay of ≥ 14 days for Cycle 2 due to unresolved treatment-related toxicity.

Management and dose modifications associated with all adverse events are outlined in Section 7.0.

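### Section 7.1.2: the Grade 3 and Grade 4 febrile neutropenia criteria overlap for every fever above 38.5 °C, and for a first or second occurrence the oxaliplatin and capecitabine instructions conflict

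*Combined protocol and SAP*

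**What the plan says.** The haematologic part of the Section 7.1.2 tables gives febrile neutropenia two rows, each with its criterion in brackets.

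- The first is headed "Grade 3 (neutropenia and fever $\geq 38.5C", that is, a fever of 38.5 °C or more. For the 1st and 2nd occurrence, both the oxaliplatin and the capecitabine columns say "Hold until resolution of fever and neutropenia to grade" 1 or lower, "then resume at 60% of current dose". For the 3rd occurrence both columns discontinue.
- The second is headed "Grade 4 (neutropenia and fever $> 38.5 C", that is, a fever above 38.5 °C. For any occurrence both columns say "Discontinue Protocol Therapy".

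The table's footnote on grading cites "National Cancer Institute Common Terminology Criteria Version 3.0". Section 7.0 says "Toxicity will be graded according to NCI-CTCAE version 4.0". The dose-limiting toxicity list in Section 3.2.1 has the entry "Neutropenic fever" with no grade and no temperature.

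**The concern.** A dose modification table works only if an event leads to one row. Here the two criteria are nearly the same, and the instructions attached to them for a first or second event cannot both be followed. A first episode with neutropenia and a fever of 39.0 °C fits both rows.

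The dose expansion cohort, 30 of the 35 evaluable patients, is open to external institutions as well as the coordinating centre (Section 3.1). Different readings at different sites are therefore foreseeable. At stake are the safety of a patient with a serious chemotherapy toxicity, the dose delivered afterwards, and how the tolerability of the regimen is described.

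**Working it through.** The plan gives no figure to reproduce on this point. The check is a comparison of the two rows, with a little arithmetic for size.

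**Inputs.** The criteria and actions come from the febrile neutropenia rows of Section 7.1.2. Starting doses are from Table 3.1: oxaliplatin 130 mg/m²; capecitabine 850 or 1000 mg/m² twice daily. The sample of 35 evaluable patients is from Section 9.1.

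**Step 1: the two sets.** Let T be the temperature in a neutropenic patient. The printed Grade 3 set is T ≥ 38.5 °C and the printed Grade 4 set is T > 38.5 °C. The Grade 4 set lies wholly inside the Grade 3 set, and the only value in Grade 3 but not in Grade 4 is T = 38.5 °C.

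**Step 2: the actions by occurrence.**

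| Neutropenia with | Rows met | 1st or 2nd occurrence | 3rd occurrence |
|---|---|---|---|
| T exactly 38.5 °C | Grade 3 only | hold, then resume at 60% | discontinue |
| T above 38.5 °C | Grade 3 and Grade 4 | resume at 60% versus discontinue: conflict | discontinue in both: no conflict |

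**Step 3: the gap in delivered dose.** For a first event in a patient still on the starting dose:

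- oxaliplatin: 0.60 × 130 = 78 mg/m² versus none;
- capecitabine: 0.60 × 850 = 510, or 0.60 × 1000 = 600, mg/m² twice daily versus none.

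The choice of row also decides which footnotes apply. Those on the Grade 3 actions include one that, after Cycle 1, lets the physician hold oxaliplatin and continue capecitabine and pembrolizumab at current dose. The Grade 4 actions carry no footnote.

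**Step 4: does anything else separate the rows?**

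- Neutrophil depth: the neutropenia rows just above define Grade 3 as 0.5 to below 1 × 10⁹/L and Grade 4 as below 0.5 × 10⁹/L. The febrile rows do not refer to these bands; the word neutropenia is ungraded in both.
- Grading standard: version 3.0 in the footnote, version 4.0 in Section 7.0, and neither definition of febrile neutropenia is reproduced.
- Dose-limiting toxicity list: ungraded, so it does not help.

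**Step 5: reach into the analyses.** Under Section 9.1.1 the primary PFS analysis keeps following patients who leave treatment because of toxicity. The secondary analysis censors them at removal from treatment, so the row chosen could move a censoring date there. One patient is 1/35 = 2.9% of the sample.

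**The case against.** The strongest reply is that the rows are keyed by grade. An investigator would grade the event under the CTC and then read one row, with the bracketed text serving only as a gloss; or the investigator would carry down the neutropenia bands printed just above. Either is a sensible way to read the table, so differing practice between sites is a risk and not a certainty. But the rows state neither route, and the first depends on a standard for which the protocol cites two versions. The inconsistency remains.

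A second reply is that the overlap hangs on one inequality sign in a table read by machine. The same table shows other damage: a misspelt neutropenia heading and a garbled range for Grade 1 thrombocytopenia. If the Grade 3 sign in the source were ≤, the rows would be mutually exclusive; if both signs were identical, the overlap would be complete. This cannot be excluded from the text, and it is why the source table must be checked first.

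A third reply is that Section 7.1 already lets investigators depart from the table in the interest of a subject's safety. That is true, and it means some variation is expected. It does not say which row an event belongs to.

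A reader might also infer that the Grade 4 row ends all study treatment. The documents do not settle that. The instruction stands in the oxaliplatin and capecitabine columns, and Section 7.1 allows pembrolizumab alone to continue when capecitabine is not tolerated.

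**Conclusion.** The point holds as an internal contradiction in one table. For neutropenia with fever above 38.5 °C, at a first or second occurrence, the printed text gives two incompatible instructions for oxaliplatin and capecitabine. It gives no conflict from the third occurrence on. The conclusion assumes that the inequality signs were read correctly.

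Three stronger inferences are not supported.

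- A reader might conclude that the primary PFS result is compromised. The primary analysis goes on following patients removed for toxicity, so the row chosen does not set their censoring. Only the secondary analysis could change, and only if the patient counts as removed from treatment.
- A reader might say that a named secondary endpoint is affected. Section 9.1.2 names safety and tolerability, with adverse events shown by type and grade. It names no discontinuation rate. What is affected is the description of tolerability.
- A reader might want a count of affected patients. The documents give no febrile neutropenia rate for this regimen. The 41-44% in Section 1.2.2 is Grade 3 or 4 neutropenia, with or without fever, in colorectal patients on a different combination. Only the weight of each event, 2.9% of 35, can be stated.

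The matter should be corrected because it is a safety instruction. No view is taken on which threshold or action is right.

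**What to change.** 1. Check both inequality signs against the source table.
2. If the overlap is confirmed, the sponsor should reconcile the two febrile neutropenia rows so that each event maps to exactly one row, and state the feature that separates them.
3. Name one CTC version for these rows and make the table footnote and Section 7.0 agree.
4. State whether the discontinuation instruction in these rows includes pembrolizumab, in light of Section 7.1.
5. Record on the CRF which criterion each event met.

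The cost is a wording amendment to one table and its grading reference, plus one CRF item. No procedures or patients are added. Febrile neutropenia events already handled under either row may need to be reviewed for consistent classification and possible deviations.
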